Data Screening: Prior to performing analyses, standard data screening/cleaning procedures will be applied. These procedures will (a) screen the data for data-entry errors, (b) check for outliers, (c) assess the extent and pattern of missing data, (d) create all summary scores needed for analysis, and (e) check that appropriate distributional assumptions are met. Assumptions will be examined using standardized residuals, influence diagnostics, and graphical displays. We will employ image quality assessment procedures to examine global and ROI-based raw and processed temporal signal-to-noise ratio, absolute and relative motion, and signal spike count. Subjects with potential outliers (>2 SDs above mean) will be flagged to determine if the time-series is valid, and if so it will remain. Otherwise it will be corrected or removed from the analysis. The final sample will be examined in a similar fashion to determine whether any subjects warrant data cleaning or exclusion from the final analysis. All analyses will be conducted using Stata software (STATA Corporation, College Station, Texas).

Missing Values: We will examine the characteristics of those subjects who drop out to identify any associations between dropout and baseline measures. These analyses will be descriptive, as we expect few dropouts. Items missing at random on survey measures will be imputed prior to calculating final scores using conditional means, estimated with a version of Buck’s method [65]. The analyses will also be repeated using only complete observations to assure that parameter estimates are not impacted by imputation.

Task fMRI: fMRI preprocessing will use standard algorithms in FSL (FMRIB’s Software Library, www.fmrib.ox.ac.uk/fsl) including distortion correction, slice-time correction, motion correction, spatial smoothing, high-pass filtering (120s) and co-registration to the MPRAGE. fMRI preprocessing will also include removal of physiological noise related to in-scanner pulse and respiration measures using RETROICOR. After preprocessing, basic subject-level BOLD time series analysis will be carried out using the general linear model (GLM) in FSL, using a canonical double-gamma hemodynamic response function (HRF) for convolution, and linear contrasts to estimate task-specific BOLD responses for each individual. Temporal derivative and extended motion parameters will be included in models when appropriate. For the block-design

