N-back task, analysis will focus on the parametric effect of increasing working memory load across four levels (linearly modeled [-3 -1 1 3]). For the cue reactivity task, the primary contrast will be smoking cues>neutral cues. For the stress task, the primary contrast will be stress > control blocks.

Subject-level statistical image maps will be transformed into a common anatomic space (Montreal Neurological Institute, MNI) for group-level analysis. Session (abstinence vs. smoking) whole brain, voxelwise analyses will test abstinence effects in brain regions specified above. The peak voxel in each significant cluster will be used to assign appropriate anatomical labels. Percent signal change within significant clusters will be utilized in regression models described below. Age, self-reported ethnicity, nicotine dependence severity (FTND), and withdrawal symptom severity will be included as covariates in the relevant statistical models. For all tests, significance will be determined using cluster $p < .05$ and voxel-height $Z > 2.33$.

Aim 1: Modeling of Days to Relapse:

The outcome associated with Aim 1 is censored time to event and the predictors are continuous measures (difference scores) extracted from ROIs associated with each neurobehavioral domain. We will test this hypothesis within each domain (working memory, cue reactivity, and stress) using Cox regression; the test statistic will be the z-score corresponding to the hazard ratio, with significance corrected for the total (8) cross domain ROIs. We will also test baseline clinical predictors and abstinence challenge-related performance measures (difference scores) for entry into each of the domain specific models.

Aim 2: Integrated Brain-Behavior Model:

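### The session maps use cluster p < .05 at a lenient Z > 2.33 height with no group-level inference method named; if that inference is parametric, the false-positive rate per map may be 2-3% or several times 5%, depending on spatial correlation

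*Combined protocol and SAP*

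**What the plan says.** All of this stands in the Statistical Analysis section of the protocol unless noted.

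- **Preprocessing (Task fMRI).** The steps include "spatial smoothing, high-pass filtering (120s) and co-registration to the MPRAGE". No smoothing kernel is given.
- **Subject level (Task fMRI).** "basic subject-level BOLD time series analysis will be carried out using the general linear model (GLM) in FSL".
- **Group level (Task fMRI).** "Session (abstinence vs. smoking) whole brain, voxelwise analyses will test abstinence effects in brain regions specified above". The threshold follows: "For all tests, significance will be determined using cluster" p < .05, with voxel height Z > 2.33. Each significant cluster is labelled by its peak voxel.
- **Onward use (Task fMRI and Aim 1).** "Percent signal change within significant clusters will be utilized in regression models described below". Under Aim 1, "the predictors are continuous measures (difference scores) extracted from ROIs associated with each neurobehavioral domain". These enter Cox models with correction for 8 ROIs; the power section sets alpha at 0.0085.

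The plan does not name a group-level model, or say whether the cluster p-value comes from random-field theory or from permutation.

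The Working Memory paragraph of the procedures lists several regions and makes left DLPFC and PCC the primary outcomes. The Cue Reactivity and Stress Reactivity paragraphs name none. The acquisition paragraph mentions ventral striatum and orbital/ventral prefrontal cortex, but only as areas of good signal. Aim 2 counts two cue regions and three stress regions without naming them.

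**The concern.** A parametric cluster p-value asks how large a cluster chance alone would produce above the forming height. The answer rests on an assumed spatial correlation, in practice Gaussian fall-off with a smoothness estimated from neighbouring voxels, and on a forming height high enough for the approximation. At Z > 2.33 clusters are wide, so any correlation reaching further than the Gaussian form allows produces chance clusters that exceed the cutoff.

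Two things would then be at stake. A chance cluster would be reported as an effect of abstinence. Its mean signal would also be carried forward as an abstinence-related predictor under an anatomical name taken from one voxel. Labels matter here because Aim 2 is built on one named region, left DLPFC, and on cue and stress regions that the plan has not named.

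**Working it through.** **1. The plan's own figures.** The cluster rule has a target (5%) but no stated operating figure to reproduce. The height converts as 1 - Φ(2.33) = 0.0099, one-sided. The neighbouring Aim 1 alpha does reproduce with a correlation-adjusted Šidák formula, 1 - 0.95^(1/8^(1-r)). Splitting the ROIs 3 + 2 + 3 (three for working memory by subtraction) gives 7 within-domain pairs out of 28. With within-domain correlation 0.55 (the plan says 0.5 to 0.6) and between-domain correlation 0 (assumed), r = 7 × 0.55 / 28 = 0.1375 and alpha = 0.0085. That alpha therefore fits a fixed set of 8 predictors.

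**2. Random-field cutoff.** For V voxels, smoothness F (FWHM in voxels) and height u:

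- Expected clusters: E[m] = (V/F³) (4 ln 2)^1.5 (2π)^-2 (u² - 1) exp(-u²/2)
- Expected voxels above u: E[N] = V (1 - Φ(u))
- Size law: β = (Γ(2.5) E[m] / E[N])^(2/3)
- The cutoff k solves 1 - exp(-E[m] exp(-β k^(2/3))) = 0.05

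Example with V = 50³ = 125,000, F = 3.0 and u = 2.33: E[m] = 4,630 × 4.617 × 0.02533 × 4.429 × 0.0662 ≈ 159; E[N] = 125,000 × 0.0099 ≈ 1,238; β = (1.329 × 159 / 1,238)^(2/3) ≈ 0.308; k = (ln(159 / 0.0513) / 0.308)^1.5 ≈ 134 voxels.

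**3. Null simulation.** The documents give neither smoothness nor correlation shape, so both are assumptions. Each row is 500 null maps, one contrast, one direction, with smoothness taken from lag-1 correlation. The Monte Carlo standard error is about 1 to 2 points for most rows. Set A uses a brain-size mask of about 88,000 voxels of 2.5 mm; set B uses the 125,000-voxel cube. In set B, long-tailed means that 40% of the variance lies in a component 2.5 times wider.

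| Assumed spatial correlation | Any false cluster, Z > 2.33 | Any false cluster, Z > 3.1 |
|---|---|---|
| A, Gaussian | 1.8% | 2.8% |
| A, 20% in a 10 mm exponential tail | 16.2% | 7.0% |
| A, 40% in a 12 mm exponential tail | 48.4% | 14.8% |
| B, Gaussian, FWHM 3 voxels | 2.8% | 2.0% |
| B, Gaussian, FWHM 4 voxels | 2.2% | 2.2% |
| B, long-tailed, base FWHM 3 | 26.8% | 9.0% |
| B, long-tailed, base FWHM 4 | 16.6% | 6.8% |

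**4. Three tasks.** The plan states no correction across the task maps. With independent maps (assumed) and one direction, the chance of at least one false cluster is 1 - 0.95³ = 14.3% at a true 5% per map, and 1 - 0.80³ = 48.8% at 20% per map.

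**5. Effect on the relapse test.** In 4,000 null runs with N = 200 and about 78% events, the Cox predictor was the mean signal of the largest cluster in a null session map (scaled-down map and threshold), with relapse independent of the map. Rejection rates were 0.8% at alpha 0.0085 and 5.2% at alpha 0.05. Both are nominal, because selection used only the session contrast.

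**6. Downstream in Aim 2.** A predictor unrelated to relapse passes the p < 0.2 screen about one time in five. If left DLPFC passes as well, its interaction is then tested at 0.05.

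**The case against.** **The method is not stated to be parametric.** Correct. Only the subject-level model is named. A Z height paired with a cluster p in an FSL linear-model plan, with no permutation mentioned, makes random-field inference the natural reading, but it remains an inference. If permutation is intended, the inflation argument falls and only the missing statement remains.

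**A reader might infer that the stated 5% is not controlled.** The documents do not support that. Under Gaussian correlation the simulated rate is below 5%, and the higher figures come from assumed tails. The 48% in particular rests on one heavy assumed shape.

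**A reader might infer that chance clusters inflate the Aim 1 error rate.** They do not (step 5). Nor is a cluster with no mean session effect necessarily useless: individual difference scores there could still relate to relapse. What is lost is the basis for calling it abstinence-induced.

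**A reader might infer that a chance cluster anywhere in the brain becomes a predictor.** The plan limits the tests to regions specified above and speaks of 8 ROIs, so a whole-brain rate overstates how often this would happen. That protects working memory, where regions are named. It does little for the five cue and stress predictors, which in practice depend on which clusters pass.

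**Raising the height to Z > 3.1 looks like a simple remedy.** It is not enough, since the long-tailed settings still gave 7-15%. It also costs sensitivity. If a session effect had d = 0.25 (an assumption, borrowed from the plan's detectable effect), the expected Z is 0.25 × √200 = 3.54. A voxel then exceeds 2.33 with probability Φ(1.21) = 0.89 but 3.1 with only Φ(0.44) = 0.67.

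**Conclusion.** The point holds in conditional form. The plan combines a lenient forming height with an unnamed group-level method. If that method is parametric, the per-map false-positive rate could lie anywhere from about 2-3% (Gaussian) to roughly 16-27% (moderate assumed long tails), or higher under heavier ones. Nothing in the documents shows which case applies, because kernel, smoothness and correlation shape are not given.

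The consequence is limited to false or mislabelled abstinence effects and to uninformative predictors that dilute power in a family whose alpha was set for 8 ROIs, chiefly for cue and stress. The loss of power has not been quantified. The primary relapse test keeps its nominal error rate.

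**What to change.** State in the Task fMRI paragraph that, for each task, cluster significance is obtained by sign-flip permutation of the abstinent-minus-smoking difference images. Use cluster mass at the planned Z > 2.33 height, or TFCE, with at least 5,000 permutations at corrected p < .05. Restrict the search to the prespecified regions wherever the plan's reference to regions specified above applies, and say that the 5% is per task map.

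Sign flipping needs symmetric errors but no assumption about spatial correlation, so it delivers the stated 5% for the mean session effect in either case above. If the listed covariates enter the group model, flip the residuals; control is then approximate.

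The cost is SAP wording and computing time, with no new data. The planned forming height can stay. Some weak clusters that parametric inference would call significant may no longer pass.

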
2. Overall Objectives - (Recruitment & Retention Pilot Study)

Aim 1: To evaluate the effects of information provision and incentives, alone and in combination, on study enrollment rates.

Hypothesis: Behavioral economic interventions will (Information provision & contingency management) will produce higher rates of enrollment compared to standard recruitment.

CHARACTERISTICS OF THE STUDY POPULATION

1. Target Population

400 healthy adult smokers between the ages of 18-65 will be enrolled in order to have 200 participants complete the study.

2. Accrual

400 male or female participants will be enrolled to have 200 complete the study at the University of Pennsylvania Center for Interdisciplinary Research on Nicotine Addiction (CIRNA). Accounting for ~50% attrition (primarily participants who are found to be ineligible during the intake session), we estimate we will need to enroll 400 eligible participants (~7 smokers per month over a 50 month period) to have up to 200 participants complete the study. Participants will first be screened over the telephone and then complete an in-person Intake Visit at the Center for Interdisciplinary Research on Nicotine Addictions to confirm final eligibility.

3. Key Inclusion Criteria

Eligible participants will be:

1. Smokers between the ages of 18 and 65, reporting consumption of at least 5 cigarettes per day for at least the past 6 months;
2. Planning to live in the area for at least the next 3 months;
3. Capable of giving written informed consent, which includes compliance with the requirements and restrictions listed in the combined consent and HIPAA form;
4. Able to communicate fluently in English (speaking, writing, and reading).

4. Key Exclusion Criteria

Subjects who present and/or self-report with the following criteria at any point during study participation will not be eligible to participate in the study:

Smoking Behavior:

1. Use of chewing tobacco or snuff or cigars;
2. Current enrollment or plans to enroll in another smoking cessation program or research study in the next 3 months;
3. Current or anticipated (within the next 3 months) use of smoking cessation medications or nicotine replacement therapy (NRT);
4. A baseline carbon monoxide (CO) reading less than 8ppm.

Alcohol/Drugs:

1. Diagnosis or treatment for alcohol or drug abuse in the past two years as reported during phone screen (e.g., alcohol, opioids, cocaine, or stimulants);

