The proposed study is a prospective observational neuroimaging investigation utilizing a pre-treatment abstinence challenge and fMRI assessment to elucidate the mechanisms underlying smoking relapse. As shown in **Figure 1**, 200 eligible consenting smokers will be scanned on two separate occasions prior to the scheduled target quit date (week 4): once during smoking satiety and once after 24 hours of biochemically confirmed abstinence (order counterbalanced). The pre-treatment scans will both include a resting BOLD MRI scan and a BOLD fMRI scan while performing validated tasks probing working memory, cue reactivity, and stress reactivity. Participants will have an individual pre-quit counseling session (week 3), and will be counseled and monitored (with biochemical confirmation) for 6 months post target quit date, with the addition of a 12 month Follow-up survey completed remotely.

Recruitment & Retention Pilot

This pilot study will utilize a randomized controlled trial design to evaluate two components of behavioral economic strategies to improve recruitment and retention. To be eligible for the pilot study participants must meet all eligibility criteria for one of the four participating studies (828958, **824061**, 824860, 828125), have a phone capable of receiving SMS messages, and consent to receive SMS messages. ~576 participants will be enrolled across the four

[figure not shown]

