participating research studies. All subjects will receive standard text messages and will be randomized to one of four groups (blocked within each study to ensure balanced groups): (1) Standard recruitment (SR): subjects will receive text messages ~2 days prior to their Intake visit with relevant information about the time, date, and location of the visit as well as contact information for study staff ("You have a study visit on [Date] at [Time]. Visit comp is \$10. Reply Y to confirm. See <http://j.mp/2222222> for reminders. Reply or appt may be canceled."); (2) SR + Information Provision (IP): Subjects will receive personalized messages designed to target injunctive norms regarding participating in research (e.g., "[Name], wondering why you should volunteer for research? Many find it a rewarding way to advance science and be a part of a community <http://j.mp/2222222>."); (3) SR + Contingency Management (CM): CM will be provided in the form of an opaque "lottery jar" with a high proportion of chips with little (\$1) monetary value. Participants draw from the lottery jar upon completion of an objectively verified target behavior (e.g., attending an Intake visit), and bonuses are often provided for continued performance [74, 75]. This strategy has been successful in augmenting visit compliance in several treatment studies [80-82]. All text reminders will be delivered using the Way 2 Health (W2H) software platform. Upon completion of all requirements for a given visit, participants will receive 5 lottery jar draws for that visit. Attendance at all visits earns participants bonus draws upon completion of the study. Failure to attend a visit without prior approval or failure to complete all visit requirements results in no draws for that visit. The lottery jar contains 500 chips: 250 say "good job," 219 have a value of \$1, 30 have a value of \$5, and 1 has a value of \$100. The study completion bonus will be 5 extra draws. Thus, at each visit, subjects will have the opportunity to make 5 draws from the lottery jar, for maximum possible earnings of \$120; (4) SR + IP + CM (IC): In this group, subjects will receive the targeted text messages and receive CM. The design of our study allows us to examine each strategy independently as well as combined to evaluate the optimal approach.

3. Study Duration

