We anticipate that abstinence-induced deficits in working memory in the Left DLPFC will predict time to relapse, as will brain responses to cues and to stress. We predict that the effect of brain responses to cues (two regions) and to stress (three regions) on days to relapse is moderated by abstinence-induced deficits in left DLPFC activity. Provided that left DLPFC deficit shows some importance in Aim 1 ($p < 0.2$), we will enter the main effect into the cue and the stress models of relapse. Further, we will test interactions of left DLPFC working memory deficit with ROIs in the cue and stress models that have also shown promise in Aim 1 ($p < 0.2$). Interactions will be tested at $\alpha = 0.05$ using the z-score corresponding to the ratio of hazard ratios (HRR).

Power and Sample Size Considerations:

Power analyses were conducted using PASS v 13.0 (Power and Sample Size, NCSS, Kaysville, UT). For Aim 1 we considered three neurobehavioral domains containing a total of 8 ROIs (predictors). We expect that predictors will be correlated, and therefore pure Bonferroni correction is too conservative [66]. In our preliminary data, within domain (e.g. working memory) correlation falls between 0.5 and 0.6 but between domains (e.g. working memory, cue reactivity) the correlation is weaker. Accounting for this weak inter-correlation, we will set alpha at $p < 0.0085$. A sample of 200 participants provides 80% power to detect a one-sample effect size of 0.25, or a hazard ratio of 1.32. Effect sizes (Cohen's d for a one-sample test) observed in our prior study [30] ranged from 0.245-0.297.

Recruitment & Retention Pilot Study:

Power is provided for our primary aim. The analysis will compare the enrollment rates between the four intervention arms, and examine main and interaction effects. For SR arm, we expect a 28% of subjects who schedule an Intake will be eligible and enroll (based on existing data across the four studies). With the proposed sample of 576, we have >80% power ($\alpha = .05$) to detect a difference between the SR arm and the IP and CM arms of 12%, corresponding to an OR of 1.75. For the interaction term, we have 80% power ($\alpha = .05$) to detect a departure from additivity of the main effects corresponding to a ratio of odds ratios (ORR) of 5.5.

3. Confidentiality

Confidentiality of the data generated in this study shall be maintained in the following ways:

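### Pilot power paragraph: 576 participants in four balanced arms detect an interaction ORR of about 2.8, not 5.5, and the >80% power fits the factorial main effects, not the SR-versus-IP/CM contrast it is attached to

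*Combined protocol and SAP*

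**What the plan says.** The Recruitment & Retention Pilot Study paragraph, under Power and Sample Size Considerations, describes the analysis: "The analysis will compare the enrollment rates between the four intervention arms, and examine main and interaction effects". It sets the control rate: "For SR arm, we expect a 28% of subjects who schedule an Intake will be eligible and enroll". It then makes two power claims for 576 participants at alpha .05:

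- a main claim of more than 80% power "to detect a difference between the SR arm and the IP and CM arms of 12%, corresponding to an OR of 1.75";
- a second claim, about interaction, of 80% power "to detect a departure from additivity of the main effects corresponding to a ratio of odds ratios (ORR) of 5.5".

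The Study Design section (Recruitment & Retention Pilot) gives the total, "576 participants will be enrolled across the four" participating studies, and the allocation, "blocked within each study to ensure balanced groups". The pilot hypothesis, under Overall Objectives, is that the behavioral economic interventions "will produce higher rates of enrollment compared to standard recruitment". The documents state no sidedness, multiplicity adjustment, dropout allowance, design effect or variance inflation for the pilot.

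**The concern.** An interaction ratio of 5.5 is very large for a 2x2 factorial with 144 per cell. Starting from 28% under SR, it would need the combined arm to enroll 68% if neither strategy worked alone, or 87% if each had an OR of 1.75. A reader would conclude that the interaction test is close to useless, although the effect of the strategies in combination is part of the pilot's Aim 1.

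The other figure misleads in the opposite direction. The >80% is attached to a comparison with the SR arm, which has only 144 participants, and the hypothesis is also framed against standard recruitment. A null result for IP against SR, or CM against SR, would be taken as backed by more than 80% power. The main relapse analysis is not affected.

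**Working it through.** **Inputs.** Total 576 in four balanced arms gives 576/4 = 144 per arm and factorial margins of 288 v 288. SR rate is 28% and alpha is .05. The effect is 12 points (28% to 40%, OR 1.714) or the stated OR of 1.75: odds 0.28/0.72 = 0.3889, times 1.75 = 0.6806, which gives 40.5%. So OR 1.75 agrees with 12 points to rounding, and both values are carried through. Assumptions: two-sided testing (one-sided also shown) and main-effect ORs of 1.0 to 2.0 behind the interaction, since the plan gives only 1.75.

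**Arm contrasts.** Power = Φ[(|p2 − p1| − z·SE0)/SE1], where SE0 uses the pooled rate and SE1 the separate rates.

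The plan's >80% is reproduced with 288 v 288 at 28% v 40%: SE0 = √(0.34 × 0.66 × 2/288) = 0.0395, SE1 = 0.0392, and (0.12 − 1.96 × 0.0395)/0.0392 = 1.09, giving 86.2%. With 144 v 144: SE0 = 0.0558, SE1 = 0.0554, and (0.12 − 1.96 × 0.0558)/0.0554 = 0.19, giving 57.6%.

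| Contrast | Two-sided, 40% / OR 1.75 | One-sided, 40% / OR 1.75 |
|---|---|---|
| SR v one arm (144 v 144) | 57.6% / 60.9% | 69.5% / 72.4% |
| SR v IP and CM pooled (144 v 288) | 69.4% / 72.8% | 79.8% / 82.5% |
| SR v all other arms (144 v 432) | 74.4% / 77.7% | 83.8% / 86.3% |
| Factorial main effect (288 v 288) | 86.2% / 88.7% | 92.0% / 93.7% |

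A logistic main-effects model gives 85.7% to 89.9% for the factorial effect, depending on whether the other factor also acts. Simulation (200,000 runs) agrees, at 40% / OR 1.75: 58.1% / 61.3% single arm, 69.6% / 72.9% pooled, 87.7% / 89.9% main effect. A single-arm contrast with SR would need 226 to 244 per arm for 80% two-sided power.

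**Interaction.** SE(log ORR) = √Σ 1/(144·p(1 − p)) over the four cells. The detectable ORR at 80% power solves ln(ORR) = (1.960 + 0.842) × SE.

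With no main effects, three cells at 28% contribute 0.03445 each and the combined cell (51.8% at the solution) contributes 0.02781. SE = √0.1312 = 0.362, and exp(2.802 × 0.362) = 2.76.

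| Main-effect ORs | 1.0 | 1.25 | 1.5 | 1.75 | 2.0 |
|---|---|---|---|---|---|
| Detectable ORR, synergy | 2.76 | 2.72 | 2.72 | 2.76 | 2.82 |
| Detectable inverse ratio, antagonism | 3.24 | 2.92 | 2.77 | 2.69 | 2.65 |

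The plan's 5.5 cannot be reproduced:

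- **Power at 5.5.** With no main effects SE = 0.368, and 1.705/0.368 − 1.96 = 2.67, giving 99.6%. With both main ORs at 1.75 it is 99.2%, and with both at 2.0 it is 98.7%. For the inverse of 5.5 it is 95.6% to 99.7%.
- **Sample size at which 5.5 has 80% power.** With no main effects, 144 × (2.802 × 0.368/1.705)² ≈ 53 per cell, rising to 64 with main ORs of 2.0 (51 to 84 for the inverse).
- **Other settings.** One-sided testing gives about 2.4 to 2.8. Using 36 per cell, one study's share, gives 8.2 to 14.1.
- **Simulation.** Power at ORR 2.75 is 80.1% with no main effects and 80.0% with main ORs of 1.75. At 5.5 it is 99.7% and 99.4%.

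On the log scale the detectable synergistic effect is about 0.6 of the stated one (ln 2.76/ln 5.5 = 1.015/1.705). With no main effects, a combined-arm rate of 51.8% is detectable, against the 68.1% that 5.5 implies. With main ORs of 1.75 the figures are 76.6% and 86.8%.

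**The case against.** The best case for the >80% figure is that it was meant for main effects. The paragraph announces main and interaction effects, gives one power sentence, then turns to the interaction term. On that reading 86-90% supports the claim, and only the naming of the contrast is at fault. Sidedness is also unstated and the hypothesis is directional: one-sided, SR against IP and CM pooled reaches 82.5% at OR 1.75, though 79.8% at exactly 12 points, and SR against all three other arms reaches 84-86%. No pairwise test is declared primary.

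Much of this stands. The figure is probably right for the test the planners had in mind. But the sentence names the SR arm, and the plan states neither a one-sided test nor pooling. Single-arm comparisons, which the aim of testing the strategies alone invites, stay below 80% even one-sided.

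On the interaction, the error is conservative: the sample detects a smaller effect than stated, and nothing shows that 5.5 drove the design. The planned study term and covariates could in principle inflate the variance. Reaching 5.5 for synergy would take roughly 2.2-fold (144/64) to 2.7-fold (144/53) inflation, and none is stated. The direction of the error limits its consequences but does not make the figure correct.

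**Conclusion.** The concern holds. The ORR of 5.5 at 80% power does not follow from 576 participants in four balanced arms. The two-sided figure is 2.7 to 2.8 for synergy, and 2.6 to 3.2 as an inverse ratio for antagonism, over main-effect ORs of 1.0 to 2.0. The >80% is correct for the factorial main effects (86-90%). It is not correct, two-sided, for SR against one arm (58-61%) or against IP and CM pooled (69-73%).

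These results rest on 144 per arm, 28% under SR, alpha .05 and no variance inflation. The one reading that rescues the named contrast is one-sided and pooled, at OR 1.75. No sidedness or main-effect assumption examined rescues the ORR. The sample size is not called into question for the factorial main effects or the interaction. What is wrong is the paragraph's account of what the pilot can detect.

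**What to change.** Reword the two power sentences:

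- State whether the tests are one- or two-sided.
- Attach the >80% to the factorial main effects of IP and CM (288 v 288). At 80% power and two-sided alpha .05, the detectable difference is about 11 points from a 28% reference (OR about 1.64). The OR of 1.75 for 12 points can stay.
- Say that each single-arm comparison with SR has about 58-61% two-sided power for the 12-point (OR 1.71 to 1.75) difference.
- Replace the ORR of 5.5 with about 2.8, stating the assumed main effects and the direction. If antagonism with no main effects is the case of interest, the inverse ratio is about 3.2. If the software run included a variance inflation or other input not shown, state it and rerun.

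The cost is two reworded sentences, with no change to sample size, allocation or conduct.
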